2.2.2. Secondary objective: diagnostic error

To demonstrate non-inferiority in the effect of evidence-based order sets versus control on the incidence of missed or delayed diagnoses for 17 common indications by primary care physicians.

Null hypothesis: evidence-based order sets increase the incidence of missed or delayed diagnoses in primary care by more than 1%.

Alternative hypothesis: evidence-based order sets do not worsen the incidence of missed or delayed diagnoses by primary care physicians compared to control, i.e. $p_A - p_B < 1\%$, with p_A and p_B being the proportion of missed diagnoses in the intervention and control groups, respectively.

Population: patients for which laboratory tests were ordered for 17 common indications by primary care physicians

Intervention: CPOE with evidence-based order sets

Comparison: CPOE without evidence-based order sets

Outcome: incidence of missed or delayed diagnoses related to the 17 indications

Time: continuously during 6 months following initial laboratory test ordering

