2.2.3. Secondary objective: test volume

To compare the effect of evidence-based order sets versus control on the number of laboratory tests ordered by primary care physicians with no restriction on the indications.

Null hypothesis: evidence-based order sets have no effect on the number of laboratory tests ordered by primary care physicians compared to control.

Alternative hypothesis: evidence-based order sets decrease the number of laboratory tests ordered in primary care by 20%.

Population: tests ordered by primary care physicians without restriction on indications

Intervention: CPOE with evidence-based order sets

Comparison: CPOE without evidence-based order sets

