4. KCELABGP_COM

6.1.1.KCELABGP_LAB

The KCELABGP_LAB database contains the data collected through the ambulatory laboratories. This database contains several tables, each containing data from the same data collections. The tables included in the KCELABGP_LAB database are TU_KCELABGP_LAB, TU_KCELABGP_LAB_INDICATN, TU_KCELABGP_LAB_TST, TU_KCELABGP_LAB_ORD_SETS, TU_KCELABGP_LAB2 and TU_KCELABGP_LAB2_LAB_TST.

TU_KCELABGP_LAB

This table contains data on each individual laboratory panel linked to an individual patient. The table includes information on date of birth, sex, reimbursement codes, physician, date of the laboratory test

panel, date of death (if applicable) and total cost of the laboratory test panel. Each row in this table represents a unique laboratory test panel and a single patient may be represented more than once.

TU_KCELABGP_LAB_INDICATN

This table contains data on the indications for each laboratory test panel. It includes data on the selected indications and the additional information provided by the physician when code 99 was used. Code 99 implied that the physicians reported that an indication was applicable outside of the 17 study indications. The exact nature of this indication was included in a free text field of the CPOE. Each row represents a unique indication. Since many laboratory test panels had more than one indication, most panels are represented multiple times.

TU_KCELABGP_LAB_LAB_TST

This table contains data on all ordered laboratory tests. Data on the laboratory test (either a Logical Observation Identifiers Name and Codes (LOINC) code or a Medidoc code), result of the test, upper limit, lower limit are included. Data on whether the result represents a normal or abnormal value is also included. The laboratory test results can be numeric or alphanumeric so that a wide variety of results are possible. Each row in the table represents a unique test. Each panel is represented multiple times as is each patient.

TU_KCELABGP_LAB_ORD_SETS

This table contains data on the selected order sets. For each possible indication, multiple order sets were developed. For instance, for the indication 'hypertension' an order set was developed for the diagnosis of hypertension, for the follow-up of hypertension and so on. This table includes more detailed information on the exact order set that was selected with respect to the indication.

TU_KCELABGP_LAB2 and TU_KCELABGP_LAB2_LAB_TST

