This table has an identical structure to the TU_KCELABGP_LAB and TU_KCELABGP_LAB_LAB_TST tables, but contains data on the patients for which cascade tests were ordered.

6.1.2.KCELABGP_GP

The KCELABGP_GP database contains information collected from the electronic health records (EHR) of the physicians on the patients included in the study. This data was collected directly from within the EHR through an electronic clinical report form (eCRF), called an eForm. Each row coincides with an item on this eForm.

TU_KCELABGP_GP

This table contains data on each eForm. Each row corresponds to an individual eForm and contains information on the patient such as sex, date of birth, date of death (if applicable), number of new diagnoses recorded through the eForm, date of the laboratory test panel, information on why the test was ordered and information on any cascade activities.

Each row in this table represents a unique eForm, so for a single patient there may be multiple rows, as for each included laboratory panel a corresponding eForm was collected. Each row has a unique identification key, named 'TXT_WRKFLOW_IDN', through which all data in this database can be linked to an individual eForm.

TU_KCELABGP_GP_DIAG

This table contains data on the new diagnoses recorded through the eForm. Each row represents a unique diagnosis and includes information on the date of the new diagnosis, information on whether the physician considered the diagnosis as related to the laboratory test (either to the indication of the laboratory test order or to the result of one of the laboratory tests in the panel), whether the new diagnosis was diagnosed timely, the name of the new diagnosis and International Classification of Primary Care (ICPC-2) or International Classification of Diseases (ICD-10) codes.

TU_KCELABGP_GP_DWNSTRM_INV

This table contains data on all the downstream investigations recorded through the eForms. Each row represents a unique downstream investigation and includes information on the patient, the type of investigation and free text additions registered by the physician.

TU_KCELABGP_GP_DOWNSTRM_REF

This table contains information on the downstream referrals recorded in the eForm. Each row represents a unique downstream referral and includes information on the patient and on the specialty of the specialist or other healthcare professional to whom was referred.

6.1.3.KCELABGP_PAT

TU_KCELABGP_PAT

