10.1.2. Secondary outcome diagnostic error

This outcome is defined in 2 independent ways.

The first is based on the physician's evaluation. During data collection, for every new diagnosis, physicians were asked whether it was related to the laboratory panel and, if so, whether the diagnosis was made correctly and timely. If the physician gives a negative answer to this question, this diagnosis is marked as 'possible diagnostic error'.

The second definition is based on a theoretical evaluation, by two independent researchers, of all occurring combinations of new diagnoses and indications for lab panels. For each combination an algorithm (see figure 2) will be applied in order to become an evaluation of 'no' or 'possible' diagnostic error. In case of dispute, a third independent researcher will be asked to resolve the evaluation. The researchers involved in this theoretical evaluation will be blinded to the allocation of the intervention until all evaluations have been made and validated.

[figure not shown]

Figure 3: Algorithm used for the theoretical evaluation of diagnostic error.

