10.2.2. Secondary outcome analysis

Diagnostic error

The proportion of patients with a missed diagnosis will be analysed by means of a logistic GEE model that includes allocated group and laboratory as factors and uses PCP as the clustering variable. An independent working correlation matrix will be used. The proportion of patients with a missed diagnosis and associated 95% confidence intervals will be estimated from the model.

The difference in proportions will be obtained by subtracting the two proportions. The associated standard error will be calculated from the rules for the variance of a difference between two independent estimates. The 95% confidence interval for the difference will be calculated.

The non-inferiority limit for missed diagnoses is 1%, i.e. the intervention will be deemed non-inferior if the difference between the allocated groups (intervention – control) is less than 1%. Therefore, the intervention will be deemed non-inferior if the upper limit of the 95% confidence interval lies below 1.

As for the primary endpoint, the analysis will be performed for all 17 study indications together. An additional analysis will be performed that only includes patients who have no indications in addition to the 17 study indications

Test volume

The total number of tests will be analysed using a GEE model for count data (Poisson or Negative Binomial to handle potential overdispersion) that includes allocated group and laboratory as factors in the model and PCP as clustering variable. No offset will be used. The number of tests per patient for each group will be estimated from the model and presented together with their associated 95%

confidence intervals. The effect of the intervention will be presented as the ratio between the two numbers with its 95% confidence interval. Statistical significance will be assessed at a significance level of 5%.

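### The physician-rated definition of diagnostic error reaches beyond the 17 indications through a gate that depends on which tests were ordered, and the SAP does not say which definition decides non-inferiority

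*SAP*

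**What the plan says.** The objective is narrow. SAP 2.2.2 gives "Outcome: incidence of missed or delayed diagnoses related to the 17 indications", and protocol 3.2.1 uses the same wording.

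SAP 10.1.2 then defines the outcome in two independent ways.

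- **First definition, physician-rated.** For each new diagnosis, "physicians were asked whether it was related to the laboratory panel and, if so, whether the diagnosis was made correctly and timely". A negative answer to the second question marks a possible diagnostic error. SAP 6.1.2, describing the diagnosis table, records relatedness as "either to the indication of the laboratory test order or to the result of one of the laboratory tests in the panel".
- **Second definition, researcher-rated.** Two researchers blinded to allocation evaluate "of all occurring combinations of new diagnoses and indications for lab panels" with an algorithm. The figure showing that algorithm is not available in the text.

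Panels may carry indications outside the study. SAP 6.1.1 says that "Code 99 implied that the physicians reported that an indication was applicable outside of the 17 study indications". SAP 6.3.2 recodes such entries where the free text clearly points to a study indication.

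SAP 10.2.2 runs one logistic GEE and one non-inferiority test, pooled over the 17 indications. It adds an analysis that "only includes patients who have no indications in addition to the 17 study indications". It does not say which of the two definitions supplies the events. Protocol 8.3.1 states that physicians know their allocation once the study starts.

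**The concern.** Under the first definition the relatedness question is a gate: only diagnoses that pass it are rated for correctness and timeliness. One way through the gate is a link to a test result, and that way exists only if the test was on the panel. The trial expects the arms to differ in exactly this respect, with a hypothesised 20% reduction in test volume (SAP 2.2.3).

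So a diagnosis unrelated to any study indication can become eligible to count as an error in one arm and not in the other, because of what was ordered and not because of how well the patient was diagnosed. The people answering are not blinded. The result feeds, or may feed, a non-inferiority claim with a margin of 1 percentage point, where a modest difference in ascertainment matters.

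Diagnoses tied only to a non-study indication are a separate and lesser problem. They also fall outside the stated outcome, but no mechanism in the documents makes them vary with test volume. They mainly add noise.

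**Working it through.** **1. Scope compared, source by source**

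| Source | What a diagnosis must relate to | Limited to the 17 indications? |
|---|---|---|
| Protocol 3.2.1, SAP 2.2.2 | the 17 indications | yes |
| SAP 10.1.2, first definition | the panel | no |
| SAP 6.1.2, diagnosis table | the order's indication, or any result on the panel | no |
| SAP 10.1.2, second definition | an indication on the panel | not stated; code 99 may be included |
| SAP 10.2.2, additional analysis | unchanged; patients are selected | patients yes, diagnoses no |

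The last row matters. Dropping patients with a code-99 indication removes the non-study-indication route. It leaves the result-linked route open for every patient who remains.

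**2. Which routes can depend on arm**

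- Link to a study indication: open in both arms whatever was ordered.
- Link to a code-99 indication: not driven by test volume.
- Link only to a test result: open only if that test was ordered, so it can depend on arm.

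**3. The plan's own figures (protocol 9.1.2)**

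Inputs are 2.5% in both arms, margin 1 point, significance level 5%, power 80%, ICC 0.025, and 42 patients per physician.

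- Per arm: 2 × 0.025 × 0.975 × (1.645 + 0.842)² / 0.01² ≈ 3014, or 6028 in total. The plan states 6032; the match is to a one-sided 5% level.
- Design effect: 1 + 0.025 × 41 = 2.025. Then 6032 × 2.025 / 42 = 290.8 physicians (plan: 290).
- With 300 × 42 = 12,600 patients, the effective number per arm is 12,600 / 2.025 / 2 = 3111.

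**4. Illustration of scale, not an estimate**

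The documents give no share of result-only events. Let r be that pool in the control arm as a fraction of the 2.5% core rate, added on top of it. Assume the pool is 20% smaller in the intervention arm. That proportionality is also an assumption.

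- Shift in the difference = −0.20 × r × 2.5 points.
- If true indication-related harm is exactly 1 point, then with x = r × 2.5% the rates are pC = 2.5% + x and pT = 3.5% + 0.8x, with d = pT − pC.
- SE = √{[pC(1 − pC) + pT(1 − pT)] / 3111}.
- Chance of declaring non-inferiority under the 95% interval rule = Φ((0.01 − d)/SE − 1.96).

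| r | Shift (points) | Chance of declaring non-inferiority at true 1-point harm |
|---|---|---|
| 0 | 0 | 2.5% |
| 10% | −0.05 | 3.2% |
| 25% | −0.125 | 4.5% |
| 50% | −0.25 | 7.2% |

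The sign is not fixed. If the pool were 20% larger in the intervention arm, the same formula would give +0.05, +0.125 and +0.25. These figures use the planned 300 × 42 patients; SAP 3.3 reports 280 physicians and 11,200 patients at the six-month check.

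**The case against.** The strongest reply is that the second definition already deals with this. It uses no physician relatedness question and no test results, and its assessors are blinded. A diagnosis the physician calls unrelated is still evaluated there. A reader might infer from the first definition that late diagnoses in patients with fewer tests are never rated at all; for the outcome as a whole that is not so. This point stands, and it limits the concern to the first definition. It does not settle the matter, because the SAP never says which definition the non-inferiority test uses.

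A reader might also infer that the arm ordering fewer tests gains an advantage, so that the plan favours non-inferiority. The documents do not support a direction.

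- Passing the gate does not make an error. The diagnosis must also be judged not correct and timely, and one revealed by an extra test may well be judged timely.
- Order sets preselect tests, and protocol 3.3.2.2 allows that better appropriateness need not lower volume.
- Protocol 3.3.2.1 gives superfluous testing as one cause of diagnostic error, so fewer such errors after less testing would be partly a real effect.

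It is also tempting to let code-99 events scale with test volume, or to quote a specific loss of power from them. Neither has a basis in the documents, which give no share or rate for such events. SAP 6.1.2 does not mention code 99 either; that comes from the laboratory tables in SAP 6.1.1, and that it reaches the physician's relatedness answer is an inference from the unrestricted wording.

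Finally, the loose link is not purely an SAP change. Protocol 8.8 already asks whether a potential missed diagnosis is related to the initial laboratory test. That shows the looseness has a history, but the conflict with the stated objective remains.

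**Conclusion.** The conflict is in the text. The stated outcome is confined to the 17 indications; the physician-rated definition is not, and one of its routes depends on panel content, which the intervention is designed to change. With raters who know their arm, ascertainment under that definition can differ between arms and can bias the non-inferiority comparison. Non-study-indication events mainly add noise.

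Direction and size are unknown. The range in the working, 0 to 0.25 points either way against a 1-point margin, rests on an assumed result-only pool of up to half the planned rate and on an assumed 20% proportional change. It shows only that the effect need not be negligible.

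The consequence depends on which definition is decisive. If it is the first, the problem bears directly on the conclusion. If it is the second, the gate is absent, though non-study indications may still enter. The SAP should settle this before anyone on the study team sees the allocation.

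**What to change.** In SAP 10.1.2 and 10.2.2, before the unblinding described in SAP 8:

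1. Name the blinded diagnosis-by-indication definition as the one used for the non-inferiority test, restricted to study indications after the code-99 recoding of SAP 6.3.2.
2. Keep the physician-rated definition, unfiltered, as a supportive analysis. Filtering it through the researchers' table would end the independence of the two definitions.
3. Report by arm the diagnoses linked only to a test result and those linked only to a non-study indication. If the relatedness field does not separate the two routes, cross-classify the physician-flagged diagnoses against the diagnosis-by-indication table.

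The cost is SAP wording and a filter on ICPC-2 codes and indications already held. The real downside is fewer events in the main analysis, by an amount that cannot be known in advance. The change removes the gate; it does not remove the general possibility that more testing leads to more recorded diagnoses, which is why the by-arm report is worth having.

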10.2. Analysis methods

10.2.1. Primary outcome analysis

Appropriateness

For the definition of the primary outcome, three numbers are relevant: (a) the number of requested tests which are appropriate, (b) the number of requested tests which are inappropriate and (c) the number of inappropriately not-requested tests. As indicated in section 5b, the latter number is only relevant for diabetes mellitus, chronic kidney disease, rheumatoid arthritis and thyroid disease. Per patient, aggregated over panels if multiple panels are available, the primary outcome is defined by the ratio $(a)/(a+b+c)$. We will refer to this ratio as the proportion of appropriate tests in the remainder.

To assess differences between the allocated groups in the proportion appropriate tests, a logistic generalized estimating equation (GEE) model will be used: of interest are the marginal proportions, not the proportions on patient, physician or PCP level.

The logistic GEE model will include the allocated group and laboratory as factors and PCP as the clustering variable. The effect of the intervention will be expressed as the difference in proportions and will be presented together with its associated 95% confidence interval. The proportion of appropriate tests in the two allocated groups will also be estimated from the GEE model and presented with their 95% confidence intervals.

Appropriateness for the composite of all study tests will be compared between intervention and control groups. Furthermore, an additional analysis will be performed that only includes patients who have no indications in addition to the 17 study indications. This additional analysis will correct for an overestimation of inappropriate tests when more than one indication is selected, including indications not under evaluation. These tests would be considered inappropriate even though they could be appropriate according to one of the other indications not being evaluated.

The analyses will be performed on all patients from all physicians according to their allocated group.

Appropriateness for each study indication separately will be performed as a secondary analysis. In this analysis we will include the number of additional indications for the panel as a factor in the analysis.

10.2.2. Secondary outcome analysis

Diagnostic error

The proportion of patients with a missed diagnosis will be analysed by means of a logistic GEE model that includes allocated group and laboratory as factors and uses PCP as the clustering variable. An independent working correlation matrix will be used. The proportion of patients with a missed diagnosis and associated 95% confidence intervals will be estimated from the model.

The difference in proportions will be obtained by subtracting the two proportions. The associated standard error will be calculated from the rules for the variance of a difference between two independent estimates. The 95% confidence interval for the difference will be calculated.

The non-inferiority limit for missed diagnoses is 1%, i.e. the intervention will be deemed non-inferior if the difference between the allocated groups (intervention – control) is less than 1%. Therefore, the intervention will be deemed non-inferior if the upper limit of the 95% confidence interval lies below 1.

As for the primary endpoint, the analysis will be performed for all 17 study indications together. An additional analysis will be performed that only includes patients who have no indications in addition to the 17 study indications

Test volume

The total number of tests will be analysed using a GEE model for count data (Poisson or Negative Binomial to handle potential overdispersion) that includes allocated group and laboratory as factors in the model and PCP as clustering variable. No offset will be used. The number of tests per patient for each group will be estimated from the model and presented together with their associated 95%

confidence intervals. The effect of the intervention will be presented as the ratio between the two numbers with its 95% confidence interval. Statistical significance will be assessed at a significance level of 5%.

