## 4 STUDY SETTING

The study will be situated in Belgian family practice. We estimate that about 124 PCPs will be included in the study (300 physicians working in 124 different PCPs). The targeted professionals are active family physicians. The study will be conducted in practices collaborating with one of three private laboratories:

1. **MCH** (Medisch Centrum Huisartsen, [name], 3000 Leuven),
2. **Anacura** ([name], 9940 Evergem), or
3. **AML** (Algemeen Medisch Laboratorium, [name], 2020 Antwerpen).

These laboratories collaborate with physicians throughout Flanders, primarily located in the region of Leuven/Flemish Brabant (MCH), East- and West-Flanders (Anacura) and Antwerp and East-Flanders (AML). Both MCH and Anacura provide laboratory services to around 500 primary care physicians, whereas AML delivers services to about 1000 physicians. All laboratories cooperate primarily with primary care physicians, but in a much smaller amount also with some private specialist practices. The study will be conducted amongst family physicians prepared to change their laboratory testing ordering from paper-based to an online CPOE.

Currently around 30% of collaborating physicians use the laboratory CPOE to order laboratory tests (personal communication 2016). All other physicians use a paper-based order form to order tests. The paper-based order forms consist of a selection of common (and less common) laboratory test, often ordered by type, such as chemistry, microbiology, haematology, etc. Figure 2 illustrates a paper-based laboratory form. An important goal will be to be able to include physicians naïve to the use of CPOE. See 8.1 for our strategies to maximise recruitment of physicians.

The study by De Sutter et al (De Sutter 2007) showed that for a series of five key tests (ureum, total protein, amylase, thrombocytes, and chloride), inappropriateness was as high as 77.5 or even 100%. For these tests, the prevalences (measured as the number of test panels including one of these test over the total number of test panels) found in their study are similar to those found at the three collaborating laboratories (data from 2016). Table 2 summarizes these prevalences. On average physicians order 14.61 tests per panel at AML, 14.2 tests at Anacura and 14.25 tests at MCH (personal communication). In the study by De Sutter et al, the average amount of tests per panel was similar, at 13.3 tests (De Sutter 2007).

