3.2. Randomisation

Participating PCPs were randomised to the intervention or to the control group. The unit of allocation is the PCP. This means that all physicians in the same practice were allocated to the same intervention and that either all or no physicians in the PCP were included in the trial. All patients cared for by the same primary care practice were exposed to the same intervention. We recruited 288 physicians on 01/12/2017 of which 8 physicians dropped out before including patients. The 280 physicians were distributed across 72 PCPs. We stratified the randomisation according to the laboratory with which they collaborated (3 strata). The level of confidence in using a CPOE was associated with the laboratory with which the PCP collaborated. This also assured that all PCPs collaborating with a laboratory were evenly distributed across both arms. Randomisation was done using a random numbers generator by the trial chief statistician. The research team will remain blinded to the allocation until after database lock. Further details on the randomisation scheme can be found in the protocol under 8.3.

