3.3. Sample size

For sample size calculations, we refer to the protocol and appendix 3 of the protocol. At the end of the six-month intervention period the planned sample size was verified based on the number of recruited physicians and the average number of patients per physician. With 280 study physicians (clusters), a sample of 12740 patients (45.5 patients on average per physician) would be necessary to have at least 80% power for the secondary outcome (diagnostic error), assuming the original intra-cluster correlation and diagnostic error rates. At that point we had recruited 11200 patients and it was deemed unfeasible to recruit an additional 1500 patients. Since most recruitments were realised by physicians who had already recruited 50 or more patients, the Steering Committee agreed that attempts to recruit additional patients should target physicians with a low number of recruited patients. Therefore, only those physicians who had not yet recruited 10 patients were allowed another month to recruit additional patients. Specific calculations regarding the sample size and the assumed intra-cluster correlations can be found in the protocol under 9.1.

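### With 72 practices and no variance estimator, small-sample correction or reference distribution named, the logistic GEE intervals are likely to be somewhat too narrow

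*SAP*

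**What the plan says.** For appropriateness, SAP 10.2.1 states: "The logistic GEE model will include the allocated group and laboratory as factors and PCP as the clustering variable". It reports the difference in proportions with a 95% confidence interval and specifies no working correlation.

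For diagnostic error, SAP 10.2.2 uses "a logistic GEE model that includes allocated group and laboratory as factors and uses PCP as the clustering variable", with an independence working correlation. The group proportions are subtracted and the standard error of the difference is built as if the two estimates were independent. Non-inferiority is declared if the upper limit of the two-sided 95% interval is below the 1% margin.

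On the number of clusters, SAP 3.2 reports: "The 280 physicians were distributed across 72 PCPs". Protocol section 4 had expected "300 physicians working in 124 different PCPs". On evenness, SAP 3.3 says that "most recruitments were realised by physicians who had already recruited 50 or more patients", and that "only those physicians who had not yet recruited 10 patients were allowed another month to recruit additional patients".

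Neither document mentions a small-sample variance correction, a t or F reference, or degrees of freedom.

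**The concern.** With an independence working correlation, the model-based GEE variance ignores clustering, so the interval in 10.2.2 is valid only with the empirical sandwich variance. That estimator is biased downward when clusters are few, and more so when their sizes are unequal, because large practices pull the fit towards themselves and leave residuals that are too small. With about 36 practices per arm and four regression parameters, the bias is modest but not negligible. A normal reference adds a little more.

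The non-inferiority decision is the more exposed of the two, because it rests wholly on where one confidence limit falls. It is also the comparison that missed its recruitment target: SAP 3.3 wanted 12,740 patients and records that "At that point we had recruited 11200 patients and it was deemed unfeasible to recruit an additional 1500 patients". SAP 10.3 then expects about 15% of patients to have no eForm. The upper limit may therefore lie close to 1%, where a slightly narrow interval can decide a safety claim.

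**Working it through.** **Inputs from the documents.** 72 practices and 280 physicians (280/72 = 3.89 per practice; the protocol's figures give 300/124 = 2.42). Three laboratories, so the model has four parameters: intercept, group and two laboratory terms. 11,200 patients (11,200/72 = 156 per practice); with 15% of eForms missing, 0.85 x 11,200 = 9,520 for diagnostic error. Error rate 2.5%, ICC 0.025 for diagnostic error, ICC 0.2 per level for appropriateness (protocol 9.1).

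**Assumed.** The CV of practice size, the split of practices over laboratories, and the practice-level ICC. The documents give none of these.

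**The plan's own figures.** Non-inferiority total = 2 x [2 x 0.025 x 0.975 x (z_alpha + z_0.80)^2 / 0.01^2]. One-sided 5% gives 6,028 (stated 6,032); one-sided 2.5% gives 7,654. The design effect at 45.5 patients per physician is 1 + 0.025 x 44.5 = 2.1125, and 6,032 x 2.1125 = 12,743 (stated 12,740). These reproduce and are not in dispute. The plan states no error rate for the GEE interval, so that has to be simulated.

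**Hand check, equal practice sizes.** Fitting four parameters to 72 practices shrinks the standard error by roughly sqrt(68/72) = 0.972. The effective cut-off is 1.96 x 0.972 = 1.905, and P(|t68| > 1.905) = 6.1%.

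**Simulation.** 72 practices, 36 per arm, three laboratories, beta-binomial outcomes, logistic GEE with independence working correlation, 8,000 to 20,000 trials per setting (Monte Carlo error about 0.2 to 0.3 points). Two-sided error at nominal 5%, uncorrected sandwich with 1.96 and a delta-method standard error:

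| Practice-size CV | Appropriateness, ICC 0.2 | Diagnostic error, ICC 0.025 |
|---|---|---|
| 0 | 6.1% | 6.4% |
| 0.5 | 6.5% | 7.2% |
| 0.8 | 7.7% | 7.7% |
| 1.0 | 8.7% | 8.7% |
| 1.3 | 10.5% | 10.3% |

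A separate run for diagnostic error (4,000 replicates, practices split 18/18/36, ICC 0.01 to 0.025) gave 5.1 to 5.6% at CV 0 and 6.3 to 7.8% at CV 0.5 to 0.8.

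In a second set of runs, practice sizes were built from 280 physicians in 72 practices, giving CVs of 0.60 to 0.98. The mean standard error was 0.88 to 0.95 of the true standard deviation. That alone implies a two-sided error of 2 x P(Z > 1.96 x 0.95) = 6.3% to 2 x P(Z > 1.96 x 0.88) = 8.5%, in line with the simulated 6.7 to 8.9%.

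**At the margin (true difference +1%, nominal 2.5%), CV 0.60 to 0.98.** False non-inferiority was 3.6 to 4.8% with the delta method and 3.3 to 4.5% with the SAP's independent-estimates rule.

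**After correction, same settings, t on 68 degrees of freedom, delta method.**
- Mancl-DeRouen: two-sided error 4.2 to 4.9%; false non-inferiority 2.3 to 2.6%. With the SAP's subtraction rule the latter was mostly 2.1 to 2.4%, and 1.9% in the lowest setting.
- Kauermann-Carroll: 5.3 to 6.5% and 2.8 to 3.4%, so only a partial correction.

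The t reference alone would not be enough. It changes 1.96 to 1.995, a widening of 1.8%, whereas the shortfall in the standard error is 5 to 12%.

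**Power, 2.5% errors in both arms, 9,520 patients.** Moving from the uncorrected sandwich with 1.96 to Mancl-DeRouen with t(68) lowers non-inferiority power from about 53% to 46% (CV 0.5, ICC 0.01) and from about 33% to 25% (CV 0.8, ICC 0.025).

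**The case against.** **The SAP never says the sandwich will be uncorrected.** True. A reader might infer that an uncorrected interval is the declared plan; the text supports only that nothing is specified. For 10.2.2 the empirical sandwich is a firm inference from the independence matrix, while the absence of a correction is inferred from silence. For 10.2.1 the working correlation is missing as well.

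**The size depends on an unknown.** Also true. A reader might infer that the trial will run at 9% error. SAP 3.3 describes unevenness between physicians, and averaging over about 3.9 physicians per practice can dampen it. With near-equal practices the excess is about one point or less; rates of 8 to 9% need a practice-size CV near 1.0.

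**Non-inferiority still meets its design level.** A reader might infer that the false-claim rate exceeds what the trial was designed to accept. It does not: 6,032 reproduces only at one-sided 5%, and 3 to 4.8% stays below that. The excess is against the 2.5% implied by the SAP's own 95% interval rule, which is the decision rule in force.

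**The SAP knew it had 72 practices.** It did, and it moved the primary analysis from patient clustering (protocol 9.3.2) to practice clustering, which is an improvement. The figure of 124 is a protocol estimate, not an SAP assumption. Knowing the number does not supply the correction.

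**The subtraction rule is conservative.** Omitting the covariance created by the laboratory terms can widen the interval and offset about 0.3 to 0.7 points of two-sided error. This is incidental and does not restore 5%.

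**Conclusion.** The point holds as a moderate weakness in the specification. If the logistic GEE is run with an uncorrected sandwich and a normal reference, two-sided error is about 6 to 8% for practice-size CVs from 0 to 0.8 and about 8 to 9% at CV 1.0. False non-inferiority at the margin is about 3 to 4.8% against 2.5%.

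Confidence is high in the direction and moderate in the size, which rests on assumed practice sizes, laboratory split and practice-level ICCs. The count models for test volume and cascade activities were not simulated, so no figure is claimed for them. The consequence is greatest for diagnostic error, where power is already reduced. For appropriateness, protocol 9.1.3 expects ample power, so a reversed conclusion is less likely, although the reported interval would still be too narrow.

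**What to change.** Before unblinding, add to SAP 10.2.1 and 10.2.2 that the logistic GEE intervals use a Mancl-DeRouen-type bias-corrected sandwich variance and a t reference with degrees of freedom equal to practices minus model parameters (72 - 4 = 68, updated if a practice contributes no data). State the working correlation in 10.2.1. Report the CV of practice size with the results so that readers can judge how much the correction mattered. Kauermann-Carroll could serve as a sensitivity analysis but should not be the main method if practice sizes are uneven.

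The change needs SAP wording and a different variance option in the analysis program, and no new data. Its price is wider intervals and about 5 to 10 percentage points less non-inferiority power when both arms have a 2.5% error rate. The SAP should say so openly, beside the shortfall already recorded in 3.3. Choosing the estimator after unblinding would be open to the charge that the result drove the choice.
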